HDU High Dependency Unit

HFOV High Frequency Oscillatory Ventilation

HRQoL Health Related Quality of Life

HSCIC Health and Social Care Information Centre

HTA Health Technology Assessment

ICNARC Intensive Care National Audit & Research Centre
ICH International Conference on Harmonisation

ICU Intensive Care Unit

MoCA-BLIND Montreal Cognitive Assessment/MoCA-Blind

NHS National Health Service

NICTU Northern Ireland Clinical Trials Unit
NIHR National Institute for Health Research

NMBD Neuromuscular Blocking Drugs

PaCO₂ Partial Pressure of Carbon Dioxide in arterial blood

PaO₂ Partial Pressure of Oxygen in arterial blood

PBW Predicted Body Weight

PEEP Positive End Expiratory Pressure

Doc No: ST06-RD01 Page **3** of **35** P/F Ratio PaO₂/FiO₂ ratio

PTSS 14 Post Traumatic Stress Syndrome Questionnaire

QoL Quality of Life RR Respiratory Rate

SADE Severe Adverse Device Effect

SAE Serious Adverse Event
SAP Statistical Analysis Plan
SD Standard Deviation

SGRQ St George's Respiratory Questionnaire
SICSAG Scottish Intensive Care Society Audit Group

SOFA Sequential Organ Failure Assessment

SOP Standard Operating Procedures

TAPSE Tricuspid Annular Plane Systolic Excursion

TSC Trial Steering Committee

USADE Unanticipated Suspected Serious Adverse Device

Effect

VFDs Ventilator Free Days

Vt Tidal Volume

VV-ECCO₂R Veno-venous Extracorporeal Carbon Dioxide Removal

Doc No: ST06-RD01

1. BACKGROUND AND DESIGN

The aim of this study proposes to deliver a multi-centre clinical trial to determine whether veno-

venous extracorporeal carbon dioxide removal (VV-ECCO₂R) and lower tidal volume mechanical

ventilation improves outcomes and is cost-effective, in comparison with standard care in

patients who are mechanically ventilated for acute hypoxaemic respiratory failure.

Hypothesizing that in adult patients who require invasive mechanical ventilation for acute

hypoxaemic respiratory failure, VV-ECCO₂R and lower tidal volume ventilation results in

reduced mortality.

This is a randomised, allocation concealed, controlled, open, pragmatic clinical and cost

effectiveness trial. The study objectives are as follows:

1.1 Primary objective

To determine whether VV-ECCO₂R and lower tidal volume mechanical ventilation in patients

with acute hypoxaemic respiratory failure decreases mortality 90 days after randomisation.

1.2 Secondary objectives

In mechanically ventilated patients with acute hypoxaemic respiratory failure we want to

determine the effects of VV-ECCO₂R on:

i. Tidal volumes

ii. Duration of mechanical ventilation

iii. Requirement for Extracorporeal Membrane Oxygenation (ECMO)

iv. Long-term mortality

v. Health Related Quality of Life

vi. Safety

vii. Cost-effectiveness in the NHS setting

viii. Long term respiratory morbidity

Patients will need to be assessed using the inclusion and exclusion criteria as set out below.

Eligibility to participate in the trial will be confirmed by a medically qualified person who is

named on the Delegation Log. The medical care given to, and medical decisions made on behalf of subjects will be the responsibility of an appropriately qualified treating physician.

Two arterial blood gas samples (ABG) will be required but these will be collected as part of standard care. The P/F ratio table in appendix 1 can be used for reference.

Patients will be eligible to participate in the study if they fulfil the following criteria:

1.3 Inclusion criteria

- Invasive mechanical ventilation using PEEP ≥ 5cmH₂O*
- Acute and potentially reversible cause of acute respiratory failure as determined by the treating physician
- Within 48 hours of the onset of hypoxaemia as defined by PaO₂/FiO₂ ≤ 20kPa**

1.4 Exclusion criteria

- Age < 16 years old
- Intubated and mechanically ventilated via an endotracheal or tracheostomy tube ≥ 7
 days (168 hours) up to the time of randomisation
- Ability to maintain Vt to ≤ 3ml/kg PBW while maintaining pH ≥ 7.2 as determined by the treating physician*
- Receiving, or decision to commence, ECMO in the next 24 hours.
- Mechanical ventilation using High Frequency Oscillatory Ventilation (HFOV) or Airway Pressure Release Ventilation (APRV)
- Untreated pulmonary embolism, pleural effusion or pneumothorax as the primary cause of acute respiratory failure.

Doc No: ST06-RD01 Page **6** of **35**

^{*}Recommended on low tidal volume ventilation ≤ 6ml/kg PBW

^{**}Requires two ABG with a PaO2/FiO2 \leq 20kPa separated by at least 6 hours. 48 hour duration to consent begins at the time of 2nd ABG demonstrating PaO2/FiO2 ratio \leq 20kPa. Site will then have a further 8 – 24 hours to randomise and administer the intervention. The onset of hypoxaemia is from time of intubation and invasive ventilation.(ABGs with PaO2/FiO2 \geq 20kPa are permitted between the two trial inclusion ABGs).

- Acute respiratory failure fully explained by left ventricular failure or fluid overload (May be determined by clinical assessment or echocardiography/cardiac output monitoring).
- Left ventricular failure requiring mechanical support
- Contra-indication to limited systemic anticoagulation with heparin
- Unable to obtain vascular access to a central vein (internal jugular or femoral vein)
- Inferior vena cava filter (if using femoral vein catheter)
- Consent declined
- Treatment withdrawal imminent within 24 hours
- Patients not expected to survive 90 days on basis of premorbid health status
- Do Not Attempt Resuscitation (DNAR) order (excluding advance directives) in place
- Severe chronic respiratory disease requiring domiciliary ventilation (except for sleep disordered breathing)
- Severe chronic liver disease (Child Pugh >11)
- Platelet count < 40,000 mm³ (Prior to catheter insertion)
- Previously enrolled in the REST trial
- Prisoners

[figure not shown]
Full details of the background to the trial and its design are presented in the protocol.

Doc No: ST06-RD01 Page **7** of **35**

^{*} This exclusion criterion relates to whether a Vt \leq 3ml/kg PBW could be achieved without the need for ECCO₂R. A tidal volume \leq 3ml/kg is unlikely to be achievable in most clinical scenarios without ECCO₂R as it is approaching dead space ventilation.

1.5 **Study Schematic Diagram**

Figure 1: Study Schematic

Doc No: ST06-RD01 Page 8 of 35

2. OUTCOME MEASURES

2.1 Primary outcome measure(s)

All cause mortality 90 days after randomisation

2.2 Secondary outcome measures

- I. Tidal volume (ml/kg PBW) at day 2 and day 3 after randomisation
- II. Ventilator free days at 28 days after randomisation
- III. Duration of ventilation in survivors after randomisation at 28 days
- IV. Need for ECMO up to Day 7
- V. Mortality rate at 28 days, 6 months and 1 year after randomisation
- VI. Health Related Quality of Life (HRQoL) at 6 months and 1 year after randomisation
- VII. Adverse event rate
- VIII. Health & Social Care Service costs at 6 months and 1 year
 - IX. St George's Respiratory Questionnaire (SGRQ) at 1 year and need for home oxygen at 6 months and 1 year after randomisation
 - X. Post Traumatic Stress Syndrome Questionnaire (PTSS-14) at 1 year after randomisation
- XI. Montreal Cognitive Assessment (MoCA-BLIND) or AD8 Dementia Screening Interview (AD8) at 1 year after randomisation

2.3 Exploratory Outcome Measures

Right heart function as determined by echocardiography during 6ml/kg PBW and ≤3ml/kg PBW tidal volume ventilation (ECHO data will only be collected at a selected number of sites).

3. DATA

3.1 CRF Forms and variables

Full details of the data to be collected and the timing of data collection are described in the trial protocol.

Doc No: ST06-RD01

A copy of the CRFs and questionnaires (e.g. Quality of Life (QoL) questionnaires) are presented in the Trial Master File.

3.2 Management of datasets

At the time of analysis:

The Data Manager in collaboration with the Study Statistician will extract data from MACRO following procedures as detailed in the SOP DM09 Database Closure/Lock and the corresponding study Data Management Plan (DMP).

3.3 Data completion schedule

Study Visits and Procedures

Clinical data will be collected during trial participants stay in the ICU up to 28 days after randomisation. For routinely collected clinical data the NHS record will be the source document and for study specific clinical measurements the CRF will be the source document.

Day 0 (baseline)

Day 0 is 24 hours prior to randomisation. If more than one value is available for this 24-hour period, the value closest but prior to the time of randomisation will be recorded. Day 0 (baseline) data collected will include but is not limited to:

- Patient demographics (date of birth, gender, measured height)
- ICNARC Case Mix Programme (CMP) number
- Scottish Intensive Care Society Audit Group (SICSAG) number
- Date/time of consent and randomisation
- Date and time of ICU admission
- Admission diagnostic category
- Assessment of functional status
- Presence of Acute Respiratory Distress Syndrome (ARDS) and aetiology
- Date/time of onset of mechanical ventilation
- The Acute Physiology and Chronic Health Evaluation score (APACHE II)

Doc No: ST06-RD01 Page **10** of **35**

- PaO₂/FiO₂ ratio (Qualifying PaO₂ /FiO₂ ratios including date/time)
- Date and time of worst PaO₂/FiO₂ ratio
- Determinants of Sequential Organ Failure Assessment (SOFA) score
- Ventilation parameters including but not limited to: Mode of ventilation, minute volume, RR, mean airway pressure, plateau pressure, PEEP
- Arterial blood gas including but not limited to FiO₂, PaO₂, PaCO₂, pH
- Date/time onset of ECCO₂R therapy (from commencement of CO₂ removal)
- Use of adjunctive therapies including Neuromuscular Blocking Drugs (NMBD) and prone position
- Echocardiography parameters including but not limited to ventricular size and function and tricuspid annular plane systolic excursion (TAPSE)

Daily Data:

Day 1 is from the time of randomisation to the end of that calendar day. If more than one value is available for this period, the value closest but after the time of randomisation will be recorded. All other daily measurements will be recorded and collected between 6-10am or as close to this time as possible, unless otherwise stated in the CRF. Daily data will be collected to day 7 and will include but is not limited to:

- Ventilation parameters including but not limited to: Mode of ventilation, minute volume, RR, mean airway pressure, plateau pressure, PEEP
- Arterial blood gas including but not limited to FiO₂, PaO₂, PaCO₂, pH
- CO₂ removal rate while on ECCO₂R therapy
- Commencement or transfer for ECMO following randomisation
- Use of adjunctive therapies including NMBD and prone positioning
- Blood product administration (blood, platelets, fresh frozen plasma, cryoprecipitate or other)
- Adverse events

Day 1 and 2:

Echocardiography parameters including but not limited to ventricular size and function and TAPSE.

Doc No: ST06-RD01 Page **11** of **35**

Day 3 and 7

• Determinants of SOFA score

28 days:

Adverse Events

6 months:

- EuroQoL-5 Dimension Questionnaire (EQ-5D-5L) (Post or telephone)
- Patients use of health and social care resources collected by resource logs

1 year:

- EQ-5D-5L (Post or telephone)
- Patients use of health and social care resources collected by resource logs
- SGRQ
- PTSS-14
- MoCA-Blind or AD8

The following data will also be collected

- Date of discontinuation of ECCO₂R and reason
- Date of discontinuation of mechanical ventilation (unassisted breathing)
- Date of critical care discharge
- Date of hospital discharge
- Date of death

Follow Up Visits and Procedures

HRQoL and Health and Social Care Service use will be assessed at 6 months and 1 year after randomisation. Patients will also be required to complete the SGRQ at 1 year.

The CTU will also collect mortality data at 1, 2 and 5 years post randomisation.

Doc No: ST06-RD01 Page **12** of **35**

3.4 Data verification

Study specific data validation checks will be implemented. The process of data validation ensuring the accuracy and quality of the data will be carried out according to SOP DM04 Data Validation and Discrepancy Management.

3.5 Data coding

The variable codings will be as specified on the CRF.

4. **DEFINITION OF TERMS**

Term	Definition
Discharge from	First discharge to a medical ward in the hospital or another hospital;
critical care	a transfer between ICUs is not considered a discharge from critical
	care.
Hospital discharge	Hospital discharge is the first date that the patient is discharged to
	home/ community, a transfer between hospitals is not considered
	as a hospital discharge
Unassisted	Extubated with supplemental oxygen, or room air, or open T-tube
breathing i.e. no	breathing, or tracheostomy mask breathing, or CPAP \leq 5 cm H ₂ O
ventilatory support	without pressure support for a calendar day. Patients receiving
	pressure support via non-invasive ventilation will be defined as
	receiving ventilatory support (except for sleep disordered
	breathing).
VFDs to day 28	The number of days from the time of initiating unassisted breathing
	to day 28 after randomisation, assuming survival for at least two
	consecutive calendar days after initiating unassisted breathing and
	continued unassisted breathing to day 28. If a patient returns to
	assisted breathing and subsequently achieves unassisted breathing

Doc No: ST06-RD01 Page **13** of **35** to day 28, VFDs will be counted from the end of the last period of assisted breathing to day 28. A period of assisted breathing lasting less than 24 hours and for the purpose of a surgical procedure will not count against the VFD calculation. If a patient was receiving assisted breathing at day 27 or dies prior to day 28, VFDs will be zero. Patients transferred to another hospital or other health care facility will be followed to day 28 to assess this endpoint.

Duration of ventilation

Counted from recruitment to the end of the last period of assisted breathing

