8.5 Trial Outcomes

- All-cause mortality 90 days after randomisation, no (%) by treatment arm, Risk ratio 95%
- Tidal Volume (ml/kg PBW) at days 2 and 3 after randomisation, mean (SD) by treatment arm, difference in mean with 95% CI
- Ventilator free days at 28 days after randomisation, mean (SD) by treatment arm,
 difference in mean with 95% CI
- Ventilation duration in survivors after randomisation at 28 days, mean (SD) by treatment arm, difference in mean with 95% CI
- Need for ECMO up to day 7, no (%) by treatment arm, Risk ratio 95% CI
- Mortality rate at 28 days after randomisation, no (%) by treatment arm, Risk ratio 95%
- Mortality rate at 6 months after randomisation, no (%) by treatment arm, Risk ratio 95%
- Mortality rate at 1 year after randomisation, no (%) by treatment arm, Risk ratio 95% CI
- SGRQ at 1 year after randomisation, Symptoms score, Activity score, Impacts score and
 Total score mean (SD) by treatment arm, difference in mean with 95% CI
- Need for home oxygen at 6 months and 1 year after randomisation, no (%) by treatment arm, Risk ratio 95% CI
- Post Traumatic Stress Syndrome Questionnaire (PTSS-14) at 1 year after randomisation,
 mean (SD) by treatment arm, difference in mean with 95% CI
- Montreal Cognitive Assessment (MoCA-BLIND) or AD8 Dementia Screening Interview (AD8) at 1 year after randomisation, mean (SD) by treatment arm, difference in mean with 95% CI
- Right heart function as determined by echocardiography during 6ml/kg PBW and
 ≤3ml/kg PBW tidal volume ventilation. Echocardiography parameters including but not
 limited to ventricular size and function and TAPSE, mean (SD) by treatment arm,
 difference in mean with 95% CI

Doc No: ST06-RD01 Page **20** of **35**

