APPENDIX 3: EXAMPLE DRAFT SUMMARY TABLES

Figure xxx. Recruitment by Site

Figure xxx. Withdrawals by Site

Table x.x.x. Baseline Characteristics at trial entry

Table A.A.A. Daseline Characteristics at that entry	ECCO₂R	Standard Care
	Intervention	n = (%)
	n = (%)	
Age (years)		
Gender Male		
Female		
Dependency prior to hospital admission		
Able to live without assistance in daily activities		
Minor assistance with some daily activities		
Major assistance with majority of/all daily activities		
Total assistance with all daily activities		
Height (cm) Measured length of patient (heel to crown)		
Predicted body weight (kg)		
Admission diagnostic category		
Central Nervous System		
Central Vascular System		
Respiratory System		
GIT Hepatology		
Renal		
Toxicology		
Haematology		
Orthopaedic		
Sepsis		
Other		
Presence of ARDS		
Aetiology of ARDS		

	ECCO₂R	Standard Care
	Intervention	n = (%)
	n = (%)	
Smoke/toxin inhalation		
Gastric content aspiration		
Near drowning		
Thoracic trauma		
Pneumonia		
Sepsis		
Cardiopulmonary bypass		
Pancreatitis		
Non-thoracic trauma		
Other		
APACHE II score		
Arterial blood gas PaCO ₂		
PaO ₂ :FiO ₂ ratio		
Worst PaO ₂ /FiO ₂ ratio		
Second qualifying PaO ₂ /FiO ₂ ratio		
Arterial pH		
Total SOFA Score		
Mode of Ventilation		
Mandatory, no spontaneous additional breaths above		
the fixed respiratory rate		
Spontaneous, no back up mandatory breaths		
Mixed, Mandatory and spontaneous breaths		
Other		
Use of Adjunctive therapies		
NMBD		
PP		
INO		
Other		
Mean airway pressure (cmH ₂ O)		
PEEP (cmH ₂ O)		
Plateau Pressure (cmH₂O)		

Doc No: ST06-RD01 Page **26** of **35**

	ECCO ₂ R Intervention n = (%)	Standard Care n = (%)
Total Respiratory Rate (Breaths/min)		
Minute volume (mL/min)		
Tidal Volume (mls/kg PBW)		

Mean (SD) presented for continuous variables and no. (%) for all categorical variables.

Table x.x.x. Treatment after Trial Entry

	ECCO₂R	Standard Care
	Intervention	n = (%)
	n = (%)	
Treatment Allocation		
Adherence to protocol-specified intervention		
No. of days on ECCO₂R*		
Reasons for ECCO ₂ R Discontinuation		
The patient's legal representative has requested		
witdrawal from the study		
There has been a safety concern about the therapy		
such that withdrawal is mandated		
 ECCO₂R therapy has been weaned 		
 7 days post randomisation 		
Escalation to ECMO has occurred		
Discontinuation of active medical treatment has		
occurred		
The patient has died		
Other		
Protocol Deviations:		
Eligibility		

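### Ventilator-free days can accrue while a patient is still on ECCO2R, because the SAP's definition of unassisted breathing ignores extracorporeal support; a second, support-free count should be pre-specified

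*SAP*

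**What the plan says.** Section 4 (Definition of Terms) equates unassisted breathing with the absence of ventilatory support and then lists qualifying states. The list opens with "Extubated with supplemental oxygen, or room air, or open T-tube" and goes on to tracheostomy mask breathing and low-level CPAP without pressure support. One substitute for the ventilator is ruled on: "pressure support via non-invasive ventilation will be defined as" ventilatory support, except in sleep disordered breathing. ECCO2R and ECMO are not mentioned.

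Two outcomes rest on this term:

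- VFDs to day 28 are "The number of days from the time of initiating unassisted breathing" to day 28, given continued unassisted breathing. The zero rule is "If a patient was receiving assisted breathing at day 27 or dies prior to day 28, VFDs will be zero".
- Duration of ventilation is "Counted from recruitment to the end of the last period of assisted breathing".

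VFDs are a secondary outcome (Section 2.2) and are analysed as a difference in means with a 95% CI (Section 8.5: "Ventilator free days at 28 days after randomisation, mean (SD) by treatment arm"). Section 3.3 lists the date ventilation stopped, which it equates with unassisted breathing, and the date ECCO2R stopped as separate items. It fixes no order between them. The treatment table in Appendix 3 gives reaching 7 days after randomisation as one reason for stopping ECCO2R, and "Escalation to ECMO has occurred" as another.

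**The concern.** ECCO2R takes over part of what the ventilator does, namely clearance of CO2, and it is the randomised treatment. Under the definition as written, a day off the ventilator but on the circuit is scored as free of ventilatory support. Standard-care patients are not allocated the circuit, so by design they cannot earn that day. Any such credit goes straight into the difference in means, in favour of ECCO2R.

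What is at stake is the interpretation of a secondary outcome. A gain in VFDs could mean that patients needed support for less time, or that one form of support had replaced another. The definition cannot tell these apart. A reader might also argue that a patient on CO2 removal is not free of ventilatory support, which leaves two defensible codings of one outcome. The trial is open, and Section 6.2 says that outcome assessors and analysts know the allocation, so the coding is better settled beforehand.

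**Working it through.** The SAP gives no figure on this point to reproduce. The check applies the definition literally to example patients and then scales the result to an arm mean.

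**1. Example patients.** Each is alive and stays off the ventilator to day 28. As written, VFDs = 28 − day the ventilator stopped. In the support-free count, VFDs = 28 − the later of ventilator stop and extracorporeal stop.

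| Ventilator stop | Extracorporeal stop | As written | Support-free |
|---|---|---|---|
| Day 3 | ECCO2R, day 7 | 25 | 21 |
| Day 5 | ECCO2R, day 7 | 23 | 21 |
| Day 6 | ECCO2R, day 7 | 22 | 21 |
| Day 10 | ECMO, day 20 (either arm) | 18 | 8 |
| Day 10 | ECMO, still on at day 28 (either arm) | 18 | 0 |

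**2. Ceiling per patient for ECCO2R.** The 7-day stop reason in Appendix 3 implies that the circuit runs to about day 7 at most. Entry requires invasive ventilation (Section 1.3), so nobody is off the ventilator at randomisation. The credit is therefore below 7 days.

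**3. Shift in the intervention-arm mean.** Shift = share of the arm with overlap × mean overlap in days. The SAP gives neither input, so both are assumed.

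| Share | 1 day | 2 days | 3 days |
|---|---|---|---|
| 1% | 0.01 | 0.02 | 0.03 |
| 5% | 0.05 | 0.10 | 0.15 |
| 10% | 0.10 | 0.20 | 0.30 |

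Only patients who survive and stay unassisted to day 28 contribute. The others score zero under either count.

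**4. Scale against precision.** Section 5 gives 560 per arm and 3% dropout: 560 × 0.97 ≈ 543. The SD of VFDs is not given; 8 to 12 days is assumed. SE = SD × √(2/543), which is 0.486 at SD 8 and 0.728 at SD 12. The 95% CI half-width is 1.96 × SE, or 0.95 to 1.43 days.

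With no true difference and a spurious shift b, the chance that the 95% CI excludes zero is 1 − Φ(1.96 − b/SE) + Φ(−1.96 − b/SE):

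- b = 0.10 days: 5.2% (SD 12) to 5.5% (SD 8).
- b = 0.30 days: 7.0% (SD 12) to 9.5% (SD 8).

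The shift is negligible at the lower value and modest at the upper one.

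**The case against.** The strongest reply is that the outcome is measured as it is named. The objective in Section 1.2 is duration of mechanical ventilation, and the outcome is "Ventilator free days at 28 days after randomisation". An extubated patient is off the ventilator. Days free of any respiratory support is a different quantity. If ECCO2R brings patients off the ventilator sooner, that is arguably part of the effect being asked about. This stands. A reader might infer that the definition is an error and should be replaced, or that duration of ventilation should be redefined in the same way. The SAP does not support either step: it contains no contradiction here, and counting extubated days as ventilation would move that outcome away from its own objective.

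Second, the overlap may hardly occur. The allocated treatment is ECCO2R together with mechanical ventilation, and the order in which the two are stopped is a matter of trial conduct that the SAP does not describe. This also stands, and it limits the size. It does not supply the missing rule.

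Third, ECMO does not make the gap one-sided. It can follow randomisation in either arm, so its credit favours one arm only if ECMO use differs, which is unknown.

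Fourth, the stakes are limited. Section 7 sets the significance level for the primary outcome only, and secondary outcomes are reported as estimates with CIs. This is true, although the main outcome table in Appendix 3 has a p-value column that covers VFDs.

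**Conclusion.** The point holds as an improvement to one secondary outcome. Read literally, Section 4 gives VFDs for days off the ventilator but on ECCO2R, and by design that credit arises only in the intervention arm. The ECMO gap is real but open to both arms.

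The size is about 0.05 to 0.3 days on the intervention-arm mean, if 5% to 10% of that arm overlapped by 1 to 3 days. Both ranges are assumptions. If nobody overlaps, the effect is nil. The 90-day mortality analysis is unaffected.

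A reader might multiply 10% by the 7-day ceiling and infer a bias of 0.7 days. That figure is out of reach: it would need every affected patient to be off the ventilator from randomisation, yet all are invasively ventilated at entry. Nor do the documents show that the VFD result will be biased. They show only that the definition does not rule it out.

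**What to change.** Leave duration of ventilation and the existing VFD definition as they are. Add to Section 4 a second VFD count, applied identically in both arms, in which days on ECCO2R count as assisted, as do days on ECMO where the stop date is available. VFDs in this count start at the later of ventilator stop and extracorporeal-support stop. Add the matching line to Section 8.5 and the Appendix 3 outcome table. Report it beside the defined result, and state that earlier liberation from support will be concluded only if the two agree.

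The cost is one additional analysis. The ECCO2R stop date is already listed in Section 3.3. An ECMO stop date is not among the listed items: Section 3.3 names only commencement of or transfer for ECMO, within daily data that end at day 7. It would have to be obtained for the few ECMO patients, including any transferred elsewhere. The second VFD figure will be slightly less favourable to ECCO2R if overlap occurs. Keeping the defined count preserves comparability with earlier ventilation trials.
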